2.1 – Our primary hypothesis is that, after reaching bilirubin levels > 2 mg/dL, patients receiving Omegaven® will reach a bilirubin level ≤ 2 mg/dL faster than patients receiving conventional fat emulsions. Additionally, while patients receiving Omegaven™ will experience a decrease in their levels of bilirubin and other hepatic enzymes over time, patients receiving conventional emulsions will maintain high levels of bilirubin and other hepatic enzymes over time.

2.2 – Patients with surgical gastrointestinal disease and cholestasis will have better clinical hepatic outcomes than patients receiving conventional emulsions.

2.3 – Since patients receiving Omegaven® will have improved immune function, they will have a lower infection rate than patients receiving conventional fat emulsions.

2.4 – Due to a better general hepatic condition, patients receiving Omegaven® will also experience lower occurrence of liver transplant, death from hepatic associated causes, and blood transfusions.

2. Background and Significance

Parenteral Nutrition Associated Liver Disease (PNALD)

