Because both Intralipid® and Liposyn® II are isotonic, both could be infused through either a central or peripheral line. Both products are compatible with parenteral nutrition solutions and were co-infused via y-site. Source container hang times varied during this period, and IFE was either infused from a single container over 24 hours or the container was changed every 12 hours per CDC recommendations. Also during this period, the administration method of PN changed. Prior to 1999, standard 0.2 micron inline filters were used routinely and only PN but not IFE could be infused through them (IFE was infused via y-site beneath the filter). After 1999, 1.2 micron filters became the standard inline filter, allowing for IFE to be filtered along with the PN solution.

Duration of Therapy

Patients remained on either Liposyn® II or Intralipid® until weaned from PN.

Discontinuation of Therapy

Patients at risk for malnutrition or resumption of PN were typically followed by the Clinical Nutrition Service for several months following discontinuation of PN.

ADDITIONAL PREDICTORS OF INTEREST

Since decisions about starting Omegaven® administration will follow a compassionate protocol, we expect that patients receiving Omegaven® will present more severe liver disease than the controls from the historical cohort. Therefore, to correct confounding biases, we anticipate the need to adjust for potential predictors of liver outcomes at baseline. Baseline will be defined as: the date that treatment starts for Omegaven® patients and on the date that patient reached bilirubin levels > 2 for soybean based fat emulsion patients.

The following predictors of liver disease will be considered:

- Baseline direct bilirubin levels.
- Diagnosis of Necrotizing Enterocolitis (vs. any other disease)
- Gender (male vs. female)
- Age (≥ 8 months vs. < 8 months)
- Gestational age
- Birth weight
- Race

To assess patients comparability, we will also descriptively explore trends in direct bilirubin level before the beginning of follow-up (start of treatment date for Omegaven® patients and date in which direct bilirubin level raised to > 2 mg/dL for control patients)

Subgroup Analysis

With exploratory purposes, we will describe safety and/or efficacy of Omegaven® in subgroups of patients including younger (vs. older) patients at baseline, patients who presented with infections (vs. who did not),

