Generally, primary safety analyses will be based on time from baseline or 30 days after baseline until two months after patients first reached direct bilirubin levels $< 2\text{mg/dL}$. Baseline will be defined as information collected at the date that treatment starts for Omegaven[®] patients and on the date that patient reached bilirubin levels > 2 for soybean oil fat emulsion patients. Information on mortality and transplant will be collected during the whole treatment with Omegaven[®] and during the whole period for which we have data available in the Andorsky et al. dataset. Primary efficacy analysis will include time from baseline until the patient normalizes bilirubin (presents three consecutive direct bilirubin $\leq 2\text{ mg/dL}$ or a direct bilirubin $\leq 2\text{ mg/dL}$ and weaned from TPN). With exploratory purpose, we will also describe the curve of the several markers for the entire period that Andorsky et al. recorded data.

Outcome/Endpoints

1. Treatment safety

Our primary outcome for treatment safety will be based on patient's essential fatty acid profile. We will compare patients before treatment with Omegaven[®] started and after treatment started (one month after treatment started until treatment stopped) with respect to the frequency with which triene/tetraene ratio > 0.2 at any time. We will also compare the occurrence any event of of hypertriglyceridemia (serum triglyceride $> 400\text{mg/dL}$) between Omegaven[®] and soybean oil fat emulsions. Primary analyses for these and all other safety outcomes will be based on a follow-up time for Omegaven[®] and soybean oil fat emulsions starting 30 days after baseline, i.e., 30 days after treatment started for Omegaven[®] patients and 2 months after the first direct bilirubin level $< 2\text{ mg/dL}$ was recorded. We will also explore comparisons including the time from baseline until the end of follow-up period.

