We will also compare nutritional outcomes of the two groups including difference in weight-for- age Z-scores and height-for-age Z-scores from baseline to the moment in which the child starts enteral feeding and to the moment in which the child receives less than 10% of their calories from PN. Comparison between study groups will be performed via t-test or Wilcoxon tests, as appropriate. Using linear regression, we will explore adjustment for baseline alternative predictors of interest. Trends over time in Z-scores will also be explored using regression with repeated measure methods.

Analysis of Efficacy of Omegaven®

The primary outcome to gain preliminary evidence of efficacy will be based on the time from baseline to normalization of bilirubin level, i.e, first time point among three consecutive in which bilirubin is < 2 mg/dL. We do not anticipate that any subject will present a rebound on direct bilirubin after normalization. However, we will describe the cohort with respect to the frequency of rebounds in bilirubin levels.

Crude comparisons of time to normalize direct bilirubin levels between Omegaven® and soybean oil fat emulsion patients will be based on Kaplan-Meier curves and log-rank tests. We will estimate hazard ratios and adjust for potential baseline confounders using Cox-proportional hazard models. For all survival analysis based on non-parametric or semi-parametric methods, we will attribute an infinite time to event (i.e., time to event larger than the largest follow-up time in the whole study population) for subjects who die or receive a liver transplant before bilirubin is normalized. Subjects who die before their bilirubin levels normalize (particularly due to liver failure) have in fact the worse outcome (infinite time to normalize bilirubin) and were not censored before reaching the endpoint of interest. Results of these analysis will be compared with results of analysis excluding subjects who die or are transplanted. Time to reach a total bilirubin of 1.2 will also be compared using survival analysis methods. Analysis of this outcome will proceed as described for direct bilirubin.

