We will also describe individual profiles over time (i.e., 2 months before baseline or birth until end of follow-up period) for all subjects using graphical methods. Trends in liver function markers over time will be explored using generalized linear models in which correlations of observations within subjects will be accounted using a generalized equations or random effects approach. In these models we will hypothesize that for both groups biochemical levels increase for all tests with equal slope before treatment. After treatment, however, levels should be decreasing for patients in the Omegaven® group. We will perform these analyses including only subjects who did not die or undergo transplantation and including all subjects but assigning for subjects who died or underwent a transplant their worse possible outcome after they died or had the transplant. Using descriptive statistics, we will also explore the association between spikes in blood tests over time and predictors including transfusions of red blood cell products and blood stream infections.

Assessment of efficacy will be also based on comparison of means (or medians) of the mean and maximum modified PELD scores of each subject across all follow-up weeks. Adjustments of these comparisons for potential confounders will be based on linear regression models. Mean rates of infection will be compared using logrank and Cox proportional hazards models. Proportions of liver transplant, mortality, and red blood cell product transfusion events between the two groups will be compared via Fisher's exact test (or Chi-square tests, when appropriate). Adjustments for potential confounders will be considered using exact stratified analysis and logistic regression models.

Missing Values

Since data will be prospectively collected in the Omegaven® group, we anticipate that data will be nearly complete, particularly for the safety outcomes. In both groups, we will explore imputing any laboratory values that are missing up to two visits in the middle of the follow-up period using linear or non-linear interpolation, as appropriate. To interpolate direct and total bilirubin, we will primarily use the two closest observations, since bilirubin could be very different in points in time located further apart from the missing observation. We will compare conclusions of analyses based on imputed values with analyses based on the available information.

Potential Study Limitations

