The main limitation of our study results from the lack of comparability between the Omegaven® and historical control groups leading to potential confounding biases in our results. Two concerns could be: a) several health care standards and reporting systems changed (possibly improved) over the last 25 years (period in which controls were enrolled); and b) Omegaven® cases may be more severe, with more

advanced PNALD than historical controls, since they will be enrolled under a compassionate use protocol. Biases due to general improvement of health care outcomes could bias against controls the actual differences in safety (such as line infections) outcomes between Omegaven® (outcomes recorded now) and historical controls (outcomes recorded in the past). Conversely, improvement in reporting systems over time would tend to bias results in opposite direction, i.e., against Omegaven®. Since both biases may occur, we would expect that they would reduce or cancel each other. Also, we will compare all safety outcomes before and after treatment started in patients receiving Omegaven®, and compare conclusions of these analyses with analyses comparing Omegaven® with historical controls. Biases due to differential severity of omegaven and historical control patients is likely to occur but decrease the potential truth effect of Omegaven®.

Biases in our efficacy estimates could also result from misclassification, since our marker or reversal of cholestasis, i.e., direct bilirubin does not accurately translate all components of liver function. Also, and more importantly biases could result from missing data, since more missing data is expected to occur in historical controls than in the Omegaven® cohort (differential pattern of missing). Misclassification due to lack of specificity or sensitivity of direct bilirubin as a marker of cholestasis would likely to be random, and thus lead to underestimation of the true effect of Omegaven® in reversal of cholestasis. Biases due to more outcomes missing in the control than in the Omegaven® group could lead to an overestimation of the effect of Omegaven®.

d. Statistical Power and Sample Considerations

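### Liver transplant and mortality are tested only as separate proportions, so a difference in transplant access or follow-up between eras could look like a drug effect

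*Combined protocol and SAP*

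**What the plan says.** Hypothesis 2.4 (Specific Aims) predicts that Omegaven patients "will also experience lower occurrence of liver transplant, death from hepatic associated causes, and blood transfusions". Section 5c, Analysis of Efficacy, tests this as follows: "Proportions of liver transplant, mortality, and red blood cell product transfusion events between the two groups will be compared via Fisher's exact test", or by chi-square. It adds: "Adjustments for potential confounders will be considered using exact stratified analysis and logistic regression models". It plans no death-or-transplant outcome, transplant-free survival or cumulative incidence for this hypothesis. The numbered efficacy item in the endpoint section is incomplete in the available text, so this reading rests on section 5c.

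The adjustment variables, introduced by "The following predictors of liver disease will be considered", are baseline direct bilirubin, necrotizing enterocolitis, gender, age, gestational age, birth weight and race. None describes calendar era, transplant listing or organ access.

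The primary efficacy analysis handles the two events together. It assigns an infinite time to normalization "for subjects who die or receive a liver transplant before bilirubin is normalized". The marker-trend analysis likewise gives both events the worst outcome.

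On follow-up, the endpoint section says: "Information on mortality and transplant will be collected during the whole treatment with" Omegaven. For the first control cohort it uses all the data held. The withdrawal criteria (Adverse Event Criteria and Reporting Procedures) remove a patient from the study when an organ is found and transplant can go ahead.

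The first controls date from the mid-1980s to 1996. A second cohort of 50 dates from 1999-2004.

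**The concern.** In end-stage liver disease the two outcomes compete. A control who dies without an organ is scored as having had no transplant, which is the favourable result on that outcome. An Omegaven patient transplanted for liver failure can be scored as alive, which is the favourable result on the other. How liver failure divides between death and transplant depends on organ access as well as on the drug, and the groups come from different periods. Potential Study Limitations concedes that "several health care standards and reporting systems changed (possibly improved) over the last 25 years", but illustrates this with safety outcomes and does not discuss transplant. The planned adjustment has no variable that could correct it.

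The recording windows pull in the same direction for mortality. Omegaven patients are observed for these events during treatment and leave at transplant, while first-cohort controls are observed for as long as data exist.

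These are the hardest clinical outcomes in the study. A lower death proportion, or a higher transplant proportion, could be credited to or held against Omegaven when it reflects organ access or length of observation.

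**Working it through.** **Checking the method.** The plan gives no power or event rates for transplant or mortality. Its only Fisher calculation is Table 5, for adverse events at 20, 25 or 30 per group. Exact two-sided Fisher power was computed as

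P(reject) = sum over x, y of Bin(x; n, p1) × Bin(y; n, p2), taken over tables with Fisher p ≤ 0.05.

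All 18 cells of Table 5 reproduce within 2 points (for example, a 45% difference from 25% gives 73.1%, 88.1% and 92.4%, against 73%, 88% and 92% stated). The same routine is used below.

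**Assumptions, none from the documents.** F is the proportion reaching liver failure, equal in both groups (no drug effect). a is the share of failures transplanted. q is the share of transplanted patients who later die and are recorded. Untransplanted failures die. Groups are equal in size: 30 is the top of the plan's power tables, and 50 is the size of the second cohort. Then

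- transplant = F × a
- death = F × [(1 − a) + a × q]
- death or transplant = F

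With F = 40%, q = 0, and a = 20% in controls and 60% with Omegaven:

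- transplant: 0.40 × 0.20 = 8% versus 0.40 × 0.60 = 24%
- death: 0.40 × 0.80 = 32% versus 0.40 × 0.40 = 16%
- either: 40% versus 40%

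**Fisher rejection (%) with no drug effect and q = 0**

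| F | Access, control / Omegaven | Transplant, n=30 | Death, n=30 | Either, n=30 | Transplant, n=50 | Death, n=50 | Either, n=50 |
|---|---|---|---|---|---|---|---|
| 30% | 30% / 50% | 3.8 | 4.5 | 2.6 | 8.1 | 7.6 | 3.1 |
| 40% | 30% / 50% | 6.5 | 6.5 | 2.6 | 12.4 | 10.9 | 3.2 |
| 30% | 20% / 60% | 14.3 | 13.3 | 2.6 | 32.5 | 25.7 | 3.1 |
| 40% | 20% / 60% | 25.5 | 21.3 | 2.6 | 49.0 | 38.7 | 3.2 |

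Fisher's test is conservative, so the undistorted reference is about 3%, as the combined outcome shows.

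**Allowing post-transplant deaths.** With q = 30%, F = 40% and access 20% / 60%, death is 0.40 × (0.80 + 0.06) = 34.4% versus 0.40 × (0.40 + 0.18) = 23.2%. Rejection for death falls to 10.2% (n=30) and 17.7% (n=50). At F = 30% it is 7.0% and 12.2%. With access 30% / 50% it is 3.4-4.3% and 5.0-6.4%. The transplant column does not change.

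**Wider range.** At 50 per group, with F from 20% to 40% and access gaps from 30% / 50% to 10% / 80%, rejection for transplant runs from 4.4% to 95.9%. For death it runs from 4.5% to 91.4% with q = 0, and from 3.4% to 52.3% with q = 30%. The combined outcome stays at 2.8% to 3.2%.

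**Unequal windows alone.** Take equal access, no drug effect, and post-transplant deaths recorded only in controls. The mortality gap is F × a × q. With F = 30%, a = 50% and q = 30%, recorded mortality is 19.5% versus 15.0%, a gap of 4.5 points. Over F 20-40%, a 30-70% and q 10-30%, the gap runs from 0.2 × 0.3 × 0.1 = 0.6 points to 0.4 × 0.7 × 0.3 = 8.4 points, always in favour of Omegaven.

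**The case against.** The strongest reply is that the documents never say transplant access changed. They mention only care standards and reporting in general, so every figure above is hypothetical, and a modest gap (30% versus 50%) at 30 per group barely moves the test. That stands, and it is why the point is put as a possibility with a range. The largest figures also use 50 per group, and the only 50 in the plan is the 1999-2004 cohort, where a tripling of access is least plausible. That stands too.

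A reader might infer that death and transplant each prevent the other. This holds one way only: transplanted patients can still die, and allowing for that roughly halves the figures for death in the 20% / 60% case.

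A reader might also infer that organ access alone could confirm hypothesis 2.4. It could not confirm the whole hypothesis. Better access raises transplants and lowers deaths, the plan reports both, and the reversal would be visible. If Omegaven truly halved liver failure from 40% to 20% with access 20% / 60%, transplants would rise from 8% to 0.20 × 0.60 = 12%, but deaths would fall from 32% to 0.20 × 0.40 = 8%. The risk lies in reading one outcome alone.

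On the windows, Omegaven patients are followed clinically for at least two months after stopping, and the design section ends the main control follow-up two months after transplant or death. But the sentence that governs mortality and transplant sets the unequal windows and names only the first cohort.

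Finally, non-comparability with historical controls is already declared the main limitation, and the study is not powered. Both are true, but neither gives the reader a comparison that is less sensitive to access.

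**Conclusion.** The concern holds in a limited form. Hypothesis 2.4 is tested only through separate transplant and mortality proportions, with no combined outcome, no access or era covariate, and unequal recording windows for the first cohort. A difference in transplant access between eras could therefore appear as a drug effect on either outcome, in opposite directions. The size depends on the assumed access gap and on post-transplant deaths. It is close to negligible for a small gap at 30 per group and substantial for a large gap at 50.

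The documents do not support saying that access did change, that the bias favours Omegaven on both outcomes, or that the main efficacy result is affected. The window problem needs no change in access and is the part most directly grounded in the text. It affects recorded mortality, by 0.6 to 8.4 points on the assumptions shown. This is a secondary comparison, and the change is worth making because it is cheap.

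**What to change.** In section 5c, Analysis of Efficacy, add death or liver transplant, whichever comes first, as a time-to-event outcome from baseline (transplant-free survival), and make it the lead comparison for hypothesis 2.4. Define one observation window from baseline that applies to the Omegaven group and to both control cohorts, and align the endpoint section with it. Keep transplant and death as reported components, using cumulative incidence of transplant and of death without transplant. Interpret them together and not as stand-alone claims. State whether hepatic death (hypothesis 2.4) or all-cause mortality (section 5c) is meant.

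The cost is mainly wording, since the plan already collects both events. If the common window runs past the end of Omegaven treatment, vital and transplant status would also have to be recorded after that point; otherwise control follow-up must be cut to match. There are two downsides. The composite weights transplant and death equally, as the primary bilirubin analysis already does. It also removes the access artefact fully only if transplanted patients would otherwise have died within the window; earlier transplants in patients who would have survived would still leave an era effect.

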Primary outcomes measured only in the Omegaven® group will include whether the triene/tetraene ratio was ever > 0.2 during the intervention period and whether the INR was ever > 2. Secondary outcomes measured only on the Omegaven® group will include platelets, prothrombin time (PT), partial thromboplastin time (PTT), and other components of the fatty acid profile. Analysis of all categorical outcomes will be based on proportions and of all continuous outcomes will be based on means or medians of the individual mean, maximum or minimum values, as appropriate, during the respective follow-up period. Comparisons between periods (pre and post-treatment) will be performed based on paired tests, parametric or non-parametric, as appropriate. We will also explore trends over time (e.g., decreasing for INR and increasing for pre-albumin) and estimate p-values via regression models using generalized estimating equations or random effects to account for within subject correlations. When describing outcomes over time, we will explore the effect of predictors of poor hepatic outcomes, such as use of antifungal agents (e.g., amphotericin) and antidiarrheal agents (e.g., loperamide), on potential spikes.

Primary outcomes measured in the Omegaven® and soybean based fat emulsion groups will include whether triglycerides were ever > 400mg/dL, whether albumin was ever > 3, any occurrence of unexpected bleeding and number of times it occurred, occurrence of any anaphylactic reaction, rate of blood stream infections as shown by positive blood cultures, rate of line infections and gram positive central venous catheter infections. Outcomes will be summarized for each study group based proportions, poisson rates, mean, minimum, or maximum over the subject follow-up period, and statistical significance of differences between groups will be estimated with exploratory purpose via Fisher's exact test, Wilcoxon or t-tests, as appropriate.

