The number of subjects included in the Omegaven® group will be based on a compassionate use protocol and not on study power considerations. The number of subjects included in the soybean oil fat emulsion historical cohort group will not be based on study power considerations but rather on the number of eligible subjects from a pre-existing cohort.

The primary safety analysis will be descriptive and not based on statistical significance. However, in Table 4 we outline power to detect several differences in the frequency of adverse events, assuming 20, 25, or 30 patients, diverse proportion of subjects with adverse event in either treatment period and not with the adverse event in the other (proportion of discordant pairs), for a two-sided 5% significance level McNemar's tests. Table 5 includes estimates of power for a Fisher's exact test when comparing Omegaven® with historical control groups, assuming diverse frequency of occurrence of the adverse event in the control group, equal number of subjects in each group, and diverse differences in proportions between Omegaven® and soybean oil fat emulsion groups.

For lower proportions of discordant pairs, we would generally attain close to 80% power in McNemar's test. Even for higher proportions of discordant pairs, assuming the high differences between before and after treatment that we expect to observe, e.g., 50% or more, 80% power can be attained in McNemar's test (Table 4). In Fisher's exact test, we will attain 80% power or more to detect differences between Omegaven® and historical controls of 45% or larger, regardless of the frequency of adverse events in each group (Table 5).

Table 4 – Power to detect varying differences in proportions before and after treatment with Omegaven® in a McNemar's test. All calculations were based on an alpha significance level of 0.05.

Difference between proportions	Proportion of discordant pairs	McNemar's Test		
		Sample size in the Omegaven™ group		
		20	25	30
30%	40%	59%	72%	81%
	60%	44%	55%	63%
50%	60%	92%	97%	99%
	80%	79%	88%	93%
80%	85%	>99%	>99%	>99%
	95%	>99%	>99%	>99%

*Calculations performed Statxact.

Table 5 – Power to detect varying differences in proportions between Omegaven® and historical control groups in a Fisher's exact test. All calculations were based on an alpha significance level of 0.05.

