Differences in the frequency of the event between Omegaven® and historical control groups	Frequency of the event in one of the comparison groups	Fisher's Exact Test		
		20	25	30
35%	5%	72%	82%	89%
	25%	49%	65%	72%
	50%	57%	68%	78%
45%	5%	89%	95%	98%
	25%	73%	88%	92%
	50%	89%	95%	98%

*Calculations performed using N-query advisor.

e. Study Organization

[name] will serve as the principal investigator. [name] will serve as the managing co-investigator. [name], [name], [name], [name], and [name] will assist with patient enrollment. Drs. [name], [name], and [name] along with the CRP staff will assist in study design and data analysis. Data collection will be done by the research nurses, with assistance from the nursing unit liaisons, the study coordinator, and research assistants in [name] lab. All individuals who assist in this function will have CITI training. The necessary CCI amendments and approvals will be obtained prior to any staff assisting in this function. The study coordinator will abstract the medical records and complete the CRFs and a careful QC visual inspection of the CRFs prior to submitting them for data entry. The Research Coordinator will complete all data entry..

f. Data and Safety Monitoring Plan

Patients will be monitored while receiving Omegaven® treatment to observe for signs of Omegaven® toxicity. At the start of Omegaven® therapy, patients will be monitored closely during and shortly after initial Omegaven® administration to observe for signs of allergic reaction and anaphylaxis. In the event the patient demonstrated signs or symptoms of allergic reaction, the Omegaven® will be discontinued and the PI and attending physician will be notified. Selected safety labs will be evaluated by attending staff

and the Study Investigators for both clinical and research purposes. Blood samples will be taken prior to the start of therapy (baseline), and thereafter in accordance with the scheduled represented in the tables below.

Reversal/Safety Study Lab Schedule:

Patient Status	Parameter	Tests to be Performed	Frequency
Inpatient/receiving Omegaven®	Direct bilirubin >2 mg/dL	PN profile, AST, GGT, CRP, lipid Panel, PT, PTT, INR, fibrinogen, EFA Panel	Weekly
	Direct bilirubin ≤2 mg/dL	PN profile	Weekly
		PN profile, AST, GGT, CRP, PT, PTT, INR, fibrinogen, EFA panel, lipid panel	Monthly
Inpatient/off Omegaven®			
		PN profile, AST, GGT, CRP, lipid Panel, PT, PTT, INR, fibrinogen, EFA Panel	one complete set of post-Omegaven labs

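### Table 4 is described as two-sided 5% McNemar power, but its figures match one-sided 5% exact power; separately, one summary sentence on Fisher power contradicts Table 5

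*Combined protocol and SAP*

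**What the plan says.** Section 5d (Statistical Power and Sample Considerations) gives two power tables. Table 4 covers before/after comparisons within the Omegaven® group for 20, 25 or 30 patients, and the text describes it as "for a two-sided 5% significance level McNemar's tests". Table 5 covers Omegaven® against historical controls by Fisher's exact test with equal groups. Both captions state that "All calculations were based on an alpha significance level of 0.05", without sidedness. The Table 4 footnote names StatXact but not the option used.

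The text draws three conclusions:

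- On McNemar: "For lower proportions of discordant pairs, we would generally attain close to 80% power".
- For differences of 50% or more, even with higher discordance: "80% power can be attained in McNemar's test".
- On Fisher: "we will attain 80% power or more to detect differences between Omegaven® and historical controls of 45% or larger, regardless of the frequency".

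Section 5c (Analysis of Safety and Tolerability) does not name a McNemar version: "Comparisons between periods (pre and post-treatment) will be performed based on paired tests, parametric or non-parametric, as appropriate".

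**The concern.** The Table 4 figures looked too high for a two-sided test at these sample sizes. If they were computed at a one-sided 5% level, a reader who takes the text at its word would overestimate what the before/after comparisons can detect, and could read too much into a non-significant result on, say, the triene/tetraene ratio or INR. Tables 4 and 5 are the plan's only power figures, so nothing else in the document corrects that impression. The Fisher sentence raised a different question: whether it agrees with the table it summarises.

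**Working it through.** **Inputs (Section 5d, Table 4).** Pairs n = 20, 25, 30; difference d between the paired proportions; proportion of discordant pairs π; alpha 0.05.

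**Method.** The number of discordant pairs is M ~ Bin(n, π). Given M = m, the pairs in the favoured direction are B ~ Bin(m, q), with q = (π + d)/(2π). Power is the sum over m and b of P(M = m)·P(B = b | m) over outcomes that reject. The one-sided exact test rejects when P(Bin(m, ½) ≥ b) ≤ 0.05. The two-sided exact test rejects when twice the smaller tail is ≤ 0.05.

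**Why sidedness matters.** Take d = 30%, π = 40%, n = 20. Then q = (0.40 + 0.30)/0.80 = 0.875 and the expected number of discordant pairs is 20 × 0.40 = 8. With m = 8, the upper tail at b = 7 is (8 + 1)/256 = 0.035.

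- One-sided, b = 7 or 8 rejects; conditional power is 8 × 0.875⁷ × 0.125 + 0.875⁸ = 0.736.
- Two-sided, 2 × 0.035 = 0.070 exceeds 0.05, so only b = 8 rejects; conditional power is 0.875⁸ = 0.344.

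Averaging over all m gives 58.5% one-sided and 45.5% two-sided. The table prints 59%.

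**Full comparison (power in %, n = 20/25/30).**

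| d / π | Printed | One-sided exact | Two-sided exact | Two-sided mid-p | Two-sided chi-square, uncorrected |
|---|---|---|---|---|---|
| 30/40 | 59/72/81 | 58.5/71.6/81.45 | 45.5/60.2/71.3 | 58.3/70.5/79.4 | 60.3/70.9/79.5 |
| 30/60 | 44/55/63 | 43.7/54.6/63.4 | 30.6/41.0/50.2 | 39.5/50.0/57.9 | 39.5/50.2/59.4 |
| 50/60 | 92/97/99 | 91.9/97.2/99.0 | 85.5/93.7/97.6 | 90.8/96.3/98.6 | 90.8/96.3/98.7 |
| 50/80 | 79/88/93 | 79.3/88.0/93.0 | 68.4/79.1/86.6 | 76.2/84.0/90.2 | 76.2/85.9/91.7 |

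One-sided exact power rounds to the printed percent in 12 of 12 cells (largest deviation 0.5 point). Two-sided exact matches none.

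Printed minus two-sided power:

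- Exact: 1.4 to 14.0 points (largest at 30/60, n = 25).
- Mid-p: 0.4 to 5.1 points.
- Uncorrected chi-square: −1.3 to 4.8 points. The negative value is 30/40 at n = 20, where print is slightly low.
- Continuity-corrected chi-square: up to 16.7 points (30/60, n = 25: 38.3 against 55).

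Closed-form two-sided normal approximations do not recover the table either. Those without continuity correction run from 6.1 points below print to 8.4 above it, the last from a Wald formula. Across all two-sided 5% versions tried, at most 7 of the 12 cells fall within 2 points of print.

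The six >99% cells do not discriminate. Under the two-sided exact test the lowest is 99.04%.

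**Control: Table 5.** Full enumeration of the two-sided 5% Fisher test, taking "Frequency of the event in one of the comparison groups" as the lower of the two frequencies, reproduces all 18 cells. The 25% row for a 45% difference gives 73.1/88.1/92.4 against the printed 73/88/92; one-sided, the first cell would be 82.3.

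**Fisher sentence.** The printed 73% (45% difference, 25% frequency, n = 20) is below 80%. Searching lower frequencies from 0 to 55% in half-point steps for a 45% difference:

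- At 20 per group, power is below 80% for lower frequencies of about 15% to 40%, with a minimum of 72.7% (27.5% against 72.5%).
- The minimum is 79.4% at 22 per group, 82.8% at 23, 88.1% at 25 and 92.3% at 30. It is not monotone (86.4% at 26) but stays above 80% from 23 to 30.

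**The case against.** The main counter-argument is that nothing depends on these tables. Section 5d says "The primary safety analysis will be descriptive and not based on statistical significance" and that neither group's size rests on power, Section 5c puts significance testing in secondary analyses, and the efficacy endpoint is untouched. This stands, and it is why the point is minor. It does not make the label correct.

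Second, the one-sided run is inferred. Two-sided exact power at a 10% level gives the same rounded figures, and so does a one-sided continuity-corrected test. This also stands: the documents do not say which option was used. But each of these explanations contradicts a two-sided 5% label.

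Third, the overstatement is material mainly under the exact or continuity-corrected test. Under mid-p, 6 of 12 cells lie within 2 points of print, and under uncorrected chi-square 7 of 12. That is fair, and it is why the size is given as a range; the plan does not name the version.

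Fourth, the two McNemar sentences are hedged summaries. The claim of power close to 80% says generally, and its weak row (30/40) already printed 59% and 72%. The sentence on differences of 50% or more says only that 80% can be attained, which remains true. Neither is an error in itself; both need qualification once the table is corrected. The Fisher sentence has no such hedge.

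**Conclusion.** The concern holds, as a minor one. Table 4 is not two-sided 5% power under any version tried; its 12 informative cells match one-sided 5% exact power (equivalently here, two-sided 10%). Its overstatement reaches 14 points for the exact test and about 5 points for mid-p or uncorrected chi-square.

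Under the two-sided exact test, no 30%-difference cell reaches 80%: power is 31% to 71%, and 80% needs 36 pairs at 40% discordance and 56 at 60%. In the 50/80 row, power at 25 pairs falls from the printed 88% to 79.1%, and 80% is first passed at 26 pairs (80.6%). Under mid-p or chi-square that row still exceeds 80% at 25 pairs.

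Independently of sidedness, the Fisher sentence is contradicted by Table 5's own 73% cell.

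These results assume the discordance model above and equal group sizes for Fisher, as Section 5d states.

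**What to change.** Recompute Table 4 as two-sided 5% and name the McNemar version in the text, the caption and Section 5c. This is cleaner than relabelling, because the plan states a two-sided test. If the exact test is chosen, the rows become 45/60/71, 31/41/50, 85/94/98 and 68/79/87, and the 80% rows stay >99%. The alternative is to keep the figures, label Table 4 one-sided 5% in both text and caption, and label Table 5 two-sided.

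Then qualify the conclusions. For the exact two-sided test:

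- 30% difference: power does not reach 80% at 20, 25 or 30 pairs.
- 50% difference with 60% discordance: at least 85%.
- 50% difference with 80% discordance: 68% at 20 pairs, 79% at 25, 87% at 30.

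Rewrite the Fisher sentence to say that a 45% difference has at least 80% power at any event frequency with 25 or more per group, and as little as about 73% with 20 per group.

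The cost is a text and table edit. Enrolment and analyses do not change; the stated power is less favourable.
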